#### *Secondary Outcomes Analysis: PDMP and Web Survey data*

For other EHR-derived secondary outcomes, we will use the same general modeling framework as for the primary outcome but will fit mixed effects logistic or linear models depending on whether the outcome was categorical or continuous.

To assess intervention effects on the frequency of checking the PDMP we will fit mixed effects Poisson regression models using data from the 12 months pre- and post-intervention. All models will include fixed effects for whether the PCP was at an intervention arm clinic, indicator for whether the month was during the intervention period, and their interaction. The models will adjust for clinician type, length of tenure in medicine, and health system indicators, and include random effects for clinic and PCP (nested in clinic) to account for within-clinic and within-provider correlation. As an exploratory analysis, we will assess whether PCP characteristics (clinician type and length of tenure) moderate the effect of the interventions using a similar process as the primary outcome.

A similar approach will be used for the web survey data, except we will fit mixed effect linear regression models using data from the pre- and post-intervention surveys. All models will include fixed effects for whether the PCP was at an intervention arm clinic, an indicator for whether the survey was the 12-month follow-up, and their interaction.

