## 5.0 Procedures Involved

### 5.1 Study Design:

The study is a clinic-randomized trial of EHR clinical decision support tools for pain treatment and opioid prescribing. We propose clinic-level randomization in order to minimize the potential for spillovers or “contamination” of the intervention across the study arms.

The randomization plan is described in the figure below. There are two dimensions to the randomization. One dimension is treatment arm within a factorial study design: some clinics will be randomized to receive “care as usual,” (Arm 1), some clinics will be randomized to receive Intervention set A (Arm 2), some clinics will be randomized to receive Intervention B (Arm 3), and some clinics will receive both Interventions A and B (Arm 4). The other dimension to randomization occurs among the clinics that are assigned to Intervention set A or B, and involves those clinics being randomized to three different conditions. 1) The clinic receives the intervention set for the entire 12 month study period (Subarm A), 2) the clinic receives the intervention set for only the first 6 months of the study period, and then reverts to “care as usual,” for Intervention set A and PMP integration without the reminder function for Intervention B (Subarm B), or 3) The clinic receives the intervention set for the first 6 months, but in the second 6 months, Intervention set A will only fire in a random half of clinical encounters and the reminder function will only fire in a random half of clinical encounters for Intervention B (Subarm C).

Exhibit 7. Randomization plan

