For the PCPs who provide this electronic authorization, Fairview IT will provide the Drug Enforcement Agency (DEA) prescriber identifier number to the PI. The list of DEA numbers will be transferred and stored via the PI's secure "BOX" account. The PI will then transfer the list of DEA numbers to the MN Board of Pharmacy, also using BOX for file transfer. The Board of Pharmacy will pull the data on monthly number of times the PMP was checked between August 2019 and September 2021, and then transfer back to the PI using BOX. The study team will analyze the PMP data on the PI's HIPAA-compliant secure server. The study team will link information on characteristics of the PCPs (i.e., provider type, clinic where they practice, treatment arm assignment, and baseline information from the web survey) with the PMP data, and then remove all identifiers from the analytic dataset. The file linking study identifiers to the PMP data will be stored separately in the PI's BOX.

- In addition, for primary care appointments with someone currently receiving a "high risk" opioid, who did not get tapered, we will assess how frequently there is a documented clinical rationale for the decision to not taper, that is consistent with the CDC's guidelines. We will do retrospective chart reviews of a random 10% sample of primary care appointments with someone currently receiving a "high risk" opioid, who did not get tapered (up to 2,000 visits). This will shed light on the appropriateness of decisions to not taper opioids among current users. For each visit that is reviewed, the study team will enter the information that is collected into a REDCap database.

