#### 5.5 Modifications to Procedures in Response to Data Monitoring Committee recommendations:

The external Data Monitoring Committee reviewed the results of the interim outcomes analysis (see Section 17.1 for details). Their letter to the PI is now added to the study IRB files. We will follow their recommendations and implement two changes to the study procedures.

Change #1: Open up the PMP Integration arm to the entire study population at the 6-month mark.

Change #2: We will not implement the secondary randomization of the intervention arm clinics into three subgroups. Instead, the clinics assigned to the “choice architecture” intervention set in Arms 3 and 4 will stay the same for months 6-12 of the study period.

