#### *Interim Outcome Analysis Plan*

The DMC is responsible for assessment of the efficacy of the interventions during the course of the study i.e. interim analyses of efficacy endpoints. The study protocol version 1.2 pre-specifies the following interim analyses: The DMC will be asked to recommend graduation to the second stage of randomization when there is clear and substantial evidence of a treatment difference. As a guideline, the Lan-DeMets spending function analog of the Pocock boundaries will be used to monitor the primary endpoint comparison for the primary aims. The statistical analysis plan is given in the protocol. In brief, we will fit mixed effects logistic regression models of the primary outcome (described below) for opioid-naïve patients using data from the 12 months of the pre-intervention period, and through December 31, 2020 (approximately 4 months of post-intervention data). These models will include fixed effects for whether or not the encounter was at a clinic in the intervention a given intervention arm or received both interventions, indicators for study month to account for secular trends, and an indicator for whether an observation takes place in an intervention arm clinic and in the post-intervention period. These models will include random effects for clinic and PCP (nested in clinic) to account for within-clinic and within-PCP correlation.

We propose a single interim analysis occurring sometime shortly after January 1, 2021, using data through December 31, 2020. The planned boundaries are given below. The advantage of using the Lan-DeMets spending function is that this permits the DMC during the course of the study to require more frequent interim analysis and preserve type I error. If more interim analyses are desired by the DMC, the Lan-DeMets spending function will be recalculated and provided with each DMC report.

Interim Analysis	Critical Z-score	Nominal One-sided p-vale	Alpha Spent
1	2.16	0.0155	0.0155
Final	2.20	0.0139	0.0095

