The analysis of the effect of the intervention on key secondary outcomes will also be provided. Should the stopping boundary be crossed at the proposed interim analysis and there is clear evidence of an intervention's effect, we would recommend the DMC to move into phase 2 of the study in which clinics in the experimental arms for that intervention would be re-randomized to continue with intervention for all opioid prescription or for only 50% of opioid prescriptions. The decision to move to phase 2 will be made separate for each intervention component (choice architecture nudge and PDMP integration/reminders).

We emphasize that data will only be available for the primary outcome in a timely manner for the opioid naïve subpopulation and, therefore, decisions on whether or not to move into stage two of randomization will be made based on that subpopulation only.

The primary outcome for the opioid-naïve subpopulation is: Whether or not an opioid is prescribed in a primary care encounter, *without* currently receiving a non-opioid alternative pain treatment (including a new order for a non-opioid pain treatment).

Key secondary outcomes to be presented to the DMC are:

- The frequency with which each PCP checks the Minnesota Prescription Drug Monitoring Program (derived from the Minnesota PDMP).
- For the opioid-naïve subpopulation, whether a CDC-recommended non-opioid treatment is ordered in a primary care visit (e.g., referral to physical therapy, prescription of an NSAID, referral to pain clinic)
- For the opioid-naïve subpopulation, the length of opioid prescriptions
- For the opioid-naïve subpopulation, the MME of opioid prescriptions

Additionally, there is a possibility that data on two secondary outcomes for the current opioid-using subpopulation will be presented to the DMC:

- Whether there was a partial reduction in the MME or prescription length of refill orders, versus a total opioid discontinuation

- Whether there was an increase in the MME/day for current opioid users with at least 50 MME/day

If at the single interim efficacy analysis, the PDMP integration/reminder intervention show substantial efficacy, we would recommend that the PDMP integration be made available to all clinics. A decision on what constitutes substantial efficacy will be made in consultation with the DMC.

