#### *Primary Outcome Analysis*

To test our primary hypotheses, we will fit mixed effects logistic regression models using data from the 12-month pre-intervention period, and the post-intervention period prior to any second-stage randomization (the model for the current “high risk” opioid group will be multinomial logistic regression due to the 3-category outcome). All models will include fixed effects for whether the encounter was at an intervention arm clinic, an indicator for whether the measurement was after the interventions began, and their interaction. The interaction is the primary measure of the intervention effect. These models include random effects for clinic and PCP (nested in clinic) to account for within-clinic and within-provider correlation. Because of the cluster-randomized design with a moderate number of clinics, residual imbalances in patient and PCP-characteristics among the randomized groups may exist. The primary analysis model will adjust for characteristics at all levels of the hierarchy including clinic-level (indicators for the four systems), PCP-level (clinician type [MD/DO, NP, or PA], sex, and length of tenure in medicine), and patient-level (age, sex, race/ethnicity, insurance status, and in-person or virtual visit). Separate models will be fit to assess the PDMP integration and choice architecture intervention and for the opioid-naïve and current, high-risk opioid users. In each model, the intervention group pools across two arms of the factorial design (e.g., the choice architecture intervention pools across arms 2 and 4) and the control condition pools across the remaining two groups (e.g., arms 1 and 3 to continue the example). A Bonferroni correction will adjust inference for multiple comparison across two different populations (opioid naïve and current, high-risk opioid users) but we will not adjust for multiple tests across the two different interventions.

As an exploratory analysis, we will assess whether PCP characteristics (clinician type and tenure in medicine) and patient characteristics (age, sex, and race/ethnicity) moderate the interventions’ effect. Tests for treatment effect heterogeneity will be implemented by adding the interaction between the potential moderator and the intervention indicator to the models for the primary

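### PMP integration was opened to all clinics at month 6, but the model for PDMP checking still treats all 12 post-intervention months as a randomised contrast, which pulls the PMP-integration effect toward the null

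*Combined protocol and SAP*

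**What the plan says.** Section 3.2 lists how often PCPs check the PMP as a secondary outcome for all PCPs. Its analysis is in section 17.3 under Secondary Outcomes Analysis: PDMP and Web Survey data: "we will fit mixed effects Poisson regression models using data from the 12 months pre- and post-intervention". The fixed effects are an indicator for being at an intervention arm clinic, an "indicator for whether the month was during the intervention period, and their interaction". Clinic and PCP random effects and some covariates complete the model. It has no month-6 cut, no time-varying exposure and no term for the second half of the year.

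Section 5.5 records two changes after the interim review. The first is "Open up the PMP Integration arm to the entire study population at the 6-month mark". The second cancels the re-randomisation of intervention clinics.

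The data request in section 5.2 covers the "monthly number of times the PMP was checked between August 2019 and September 2021". The interim plan in section 17.1 uses data "through December 31, 2020 (approximately 4 months of post-intervention data", which dates activation to about September 2020.

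The primary-outcome model in section 17.3 has a different window: 12 pre-intervention months and "the post-intervention period prior to any second-stage randomization".

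**The concern.** Once integration is open to everyone, Arms 1 and 2 no longer lack it, yet the model still codes them as unexposed. The one interaction then averages six months of full contrast with six months of reduced or absent contrast, and the result would be read as integration versus no integration. The section describes its purpose as assessing intervention effects and never defines an early-versus-delayed comparison.

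The text is current. The committee's recommendations entered in revision 4 (February 2021). Revision 5 (May 2022) changed the analysis plan before analysis began, and the 12-month window is still there.

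At stake is the secondary outcome closest to what PMP integration does. A real effect could be reported as much smaller than it was while the randomised comparison was intact, or be missed.

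**Working it through.** **Are the crossed-over months in the data?** Four months of follow-up by December 31, 2020 puts activation at about 1 September 2020. Month 6 then ends around the end of February 2021, and months 7-12 run from about March to August 2021. The PMP extract runs to September 2021, so about 6 of the 12 post months follow the opening.

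**What does the interaction estimate?** The plan states no rate, effect size or power for PDMP checks, so there is no figure to reproduce. Assume:

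- equal volume each month, and 6 + 6 post months;
- arms pooled as 3 + 4 versus 1 + 2. Section 17.3 states pooling for the primary models; the PDMP paragraph does not repeat it;
- a true rate ratio RR for integration, sustained in Arms 3 and 4 for all 12 months;
- Arms 1 and 2 reach a share s_m of the log effect in month m of months 7-12.

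With a log link and one post indicator:

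estimated RR = 12·RR / (6 + Σ RR^s_m), summing over months 7-12

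share of log effect kept = ln(estimated RR) / ln(RR)

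Worked case, RR = 1.5 and s = 1 throughout: 12 × 1.5 / (6 + 6 × 1.5) = 18/15 = 1.20; ln 1.20 / ln 1.5 = 0.450.

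| Control uptake in months 7-12 | RR 1.2 | RR 1.5 | RR 2 | RR 3 | Kept |
|---|---|---|---|---|---|
| Full and immediate (s = 1) | 1.09 | 1.20 | 1.33 | 1.50 | 48-37% |
| Rising over 3 months (s = 1/3, 2/3, then 1) | 1.11 | 1.25 | 1.43 | 1.67 | 56-47% |
| Rising in equal steps over 6 months (s = 1/6 to 1) | 1.14 | 1.32 | 1.58 | 2.01 | 70-63% |
| Access only, half the log effect (s = 0.5) | 1.15 | 1.35 | 1.66 | 2.20 | 74-72% |
| Access only, a quarter (s = 0.25) | 1.17 | 1.42 | 1.83 | 2.59 | 87% |
| Access only, a tenth (s = 0.1) | 1.19 | 1.47 | 1.93 | 2.84 | 95% |

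The last three rows matter because section 5.5 does not say whether the reminder was opened along with access. Section 5.1 had treated "PMP integration without the reminder function for Intervention B" as a separate condition, and section 17.1 says only "we would recommend that the PDMP integration be made available to all clinics". If the reminder stayed in the original arms, months 7-12 retain a reminder contrast.

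**Simulation.** Counts were simulated for 48 clinics with 10 PCPs each, assuming 8 checks per PCP per month and assumed clinic and PCP variances (4,000 runs; the group-wise post/pre log ratio stood in for the mixed-model interaction).

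| True RR | Months 1-6 only | 12 months, s = 1 | 12 months, s = 0.5 |
|---|---|---|---|
| 1.25 | 1.249 | 1.111 | 1.183 |
| 1.5 | 1.506 | 1.205 | 1.347 |
| 2.0 | 2.001 | 1.338 | 1.657 |

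At RR 1.5, illustrative power was about 99% with months 1-6, 48% with 12 months and full uptake, and 86% with 12 months and half uptake. These power figures depend wholly on the assumed variances. The simulation confirms the algebra; it does not test the uptake assumptions.

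**Does the effect have to be sustained?** Let the effect in Arms 3 and 4 be a in months 1-6 and b in months 7-12, with controls gaining a in months 7-12. The estimate is (a + b)/(1 + a).

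- Fading use, a = 1.5 and b = 1.0: 2.5/2.5 = 1.00, against a true 12-month average of (1.5 + 1.0)/2 = 1.25.
- Growing use, a = 1.2 and b = 1.5: 2.7/2.2 = 1.23, against (1.2 + 1.5)/2 = 1.35.

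Both estimates lie below the true 12-month effect of access versus no access. In the growth case, however, the estimate exceeds the months 1-6 value of 1.2.

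**The case against.** The strongest reply is that bias presupposes a target. As a comparison of early with delayed access, the 12-month estimate is valid. That is correct, but the plan does not define that comparison, and a reader would take the coefficient as the effect of integration.

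A second reply is that the size is undetermined, and this stands. The documents fix neither the effect nor what crossed over nor how quickly controls took it up. If access without the reminder does little, only 5-13% of the log effect is lost; if controls do not respond at all, nothing is lost. The statement that the estimate is smaller than the months 1-6 effect also needs the effect in the original arms not to grow, as the 1.23 versus 1.2 case shows.

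A third is that consequences are limited. This is one secondary outcome for one of two interventions, and the interim review was to see PDMP checking on data from before the opening. That is fair and bears on the grading, but nothing commits the study to reporting the uncontaminated contrast as its final result.

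Finally, the primary model's cut-off might be thought to cover this. It does not: the PDMP paragraph sets its own 12-month window, and the cut-off is tied to a randomisation that section 5.5 cancels.

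**Conclusion.** The concern holds. Sections 5.5 and 17.3 are inconsistent as written, and nothing elsewhere repairs the PDMP model. For the effect of having versus not having integration, the 12-month interaction is attenuated whenever control clinics respond to access in the same direction. Across the first four uptake patterns tabulated, with a sustained effect in Arms 3 and 4, 37-74% of the log effect is kept; that is an illustration under assumed rate ratios, not a bound. Confidence is high on the inconsistency and on the conditional direction, and low on the size.

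The choice-architecture contrast is not diluted this way, because both of its pooled sides gain access equally, barring an interaction between the two interventions. The point should be fixed before the PDMP result is reported; it does not touch the prescribing results except through the undefined end date noted under the fix.

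**What to change.** In the PDMP paragraph of section 17.3, for the PMP-integration contrast, do one of the following:

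- end the post period at the date integration was opened to all clinics; or
- keep 12 months, add an indicator for months 7-12 and its interaction with arm, and name the months 1-6 interaction as the effect estimate.

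The second is preferable if the reminder was not opened, since it keeps the remaining reminder contrast as a separate estimate. Section 17.3 already uses a comparable extra period indicator for the second-stage randomisation that did not go ahead.

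Also:

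- State in section 5.5 whether the reminder was opened along with access, and give the date.
- State in the PDMP paragraph that arms are pooled as in the primary models.
- For the PMP contrast in the primary and EHR secondary models, replace the cut-off tied to the cancelled randomisation with the same month-6 date. Section 17.2 already describes the Primary Aim as months 1-6.
- The choice-architecture contrast may keep 12 months for PDMP checks, with a note that PMP access was universal in the second half.

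Two labelling points: the 12-month survey falls wholly after the opening, so its PMP contrast should be reported as early versus delayed access; and section 5.5 places choice architecture in Arms 3 and 4, which must be reconciled with sections 5.1 and 17.3 (Arms 2 and 4).

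The cost is SAP wording and a refit. The PMP extract is monthly, so no new data are required.

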#### All PCPs, including visits with opioid-naïve and current opioid-using patients:

- 1) The frequency with which PCPs check the PMP.
- 2) PCP satisfaction with decision support

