- Data from the shared EHR of Fairview and UMP will be used for analysis. These data are already collected as part of clinical care, and the research team will access these data via the University of Minnesota's Informatics Consulting Service. The data that the Informatics Consulting Service already has on hand will be augmented with additional EHR data on the activation of the study's EHR alerts and the engagement with these alerts, along with data from the legacy HealthEast (which is now part of Fairview) Epic system which are not currently received by the Informatics Consulting Service. Fairview IT will share those data with the Informatics Consulting Service, who will merge it with the other EHR data that the Informatics Consulting Service already has. All of these data will be stored and accessed only on the ICS's secure data shelter.
- We will conduct retrospective chart reviews of the visit records for all visits where someone currently receiving a "high risk" opioid had an order that would reduce MME by no greater than 20% relative to the current prescription. The study team has already created the chart review tool that will be used. These chart reviews will ascertain whether there is any documentation of the clinical rationale for tapering that is consistent with the

CDC's guidelines. Each month during the 12-month study period, the study team will receive a new data extract from the AHC-IE, from which we will identify the relevant visits. We will record the Medical Record Number and visit date and store them in a database in the AHC-IE's server. At the conclusion of the 12 month study period, all of these files will be destroyed.

The PI will share that identifying information with the co-Investigator who will lead the chart reviews. For each visit that is reviewed, the study team will enter the information that is collected into a secure REDCap database. These data will then be shared with the ICS staff, who will link it to the EHR data in the ICS' secure data shelter.

- Data on the number of times per month each PCP checks the PMP, or has an assigned delegate check the PMP on their behalf, will be taken directly from the Minnesota PMP. The PMP data are held by the state of Minnesota Board of Pharmacy. The study team will email the PCPs in the study asking for electronic authorization to access their data on how frequently they and their delegates check the Minnesota PMP between August 2019 and September 2021.

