## **11.0 Number of Participants**

### **11.1 Number of Participants to be Consented:**

We expect to enroll approximately 300-350 PCPs in both the baseline and follow-up web surveys.

We expect that 400-450 PCPs will be included in the final analytic samples for the analysis of EHR data and PDMP data.

We expect that 20,000 charts will be reviewed in the retrospective chart reviews of primary care visits with current opioid users.

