### Futility Analysis

There will be no formal futility analyses presented to the DMC. Given that these interventions have small potential adverse effects, the DMC will NOT be asked to recommend early termination for futility.

17.2 Power Analysis: The proposed design has sufficient power to detect clinically meaningful changes in opioid prescription practices from the main effects of the two interventions and the control group (10). All power calculations assume a two-sided test at the 0.05 significance level. Power for the Primary Aim (comparison of intervention arms to the control during months 1-6) is shown in Exhibits 2a-b assuming a total of 48 clinical are randomized (equal allocation between Arms 1-4) with a conservative estimate of 10 providers per clinic (~12 providers per clinic in the FHS/UMP system). The range of the number of visits eligible and the percentage of visits with an opioid prescription in the control arm (for both the opioid-naïve and opioid-using populations) were based on preliminary data from the EHR from a subset of clinics that will be randomized. Meeker et al. (1) assumed an intra-clinic correlation of 0.05 but that encounters within the same provider were not further correlated. We assumed the correlation for visits within the same clinic (but with different providers) was 0.025 and the within-provider correlation would be 0.075 as well as considering a more conservative scenario (correlation given on the logistic scale (11)). We assumed a 5% and 17% prescription rate in the control arm for the opioid-naïve and opioid-using populations, respectively, based on preliminary analysis of opioid prescribing in Fairview primary care clinics, and based on published research (12). We considered a difference in the percentage of eligible encounters with an opioid prescription between the intervention and control groups of 3.5% and 5% to be of clinical interest in the two populations. Exhibits 8 and 9 demonstrate that we have sufficient power across a wide range plausible scenarios and maintain adequate power even under smaller effect sizes. These calculations are also conservative as they assume 48 clinics, whereas we expect to enroll over 50 clinics.

We also have sufficient power to detect differences between 2.5 to 4 percentage points across the two intervention sets during the first 6 months of the intervention.

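### The Poisson model for monthly PMP checks has no term for extra-Poisson variation or unequal change, so its confidence intervals will be too narrow if either is present

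*Combined protocol and SAP*

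**What the plan says.** Section 3.2 lists "The frequency with which PCPs check the PMP" as a secondary outcome for all PCPs. Section 5.2 describes the source as "Data on the number of times per month each PCP checks the PMP, or has an assigned delegate check the PMP on their behalf", so the data are monthly counts per PCP, available for PCPs who authorise access. Section 17.1 includes the outcome among several key secondary outcomes to be presented to the DMC.

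For the analysis, section 17.3 states: "we will fit mixed effects Poisson regression models using data from the 12 months pre- and post-intervention". The fixed effects are arm, an "indicator for whether the month was during the intervention period, and their interaction", plus clinician type, tenure and health system. The models "include random effects for clinic and PCP (nested in clinic) to account for within-clinic and within-provider correlation".

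The documents do not mention overdispersion, a negative binomial or quasi-Poisson model, an observation-level effect, period-level random effects or robust standard errors. They give no fallback if the Poisson variance does not fit.

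**The concern.** The intervention effect is a before/after contrast within PCPs, compared between arms. Clinic and PCP intercepts absorb stable differences in level, but those differences drop out of a before/after ratio. Two sources of error do not drop out:

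- month-to-month variation in a PCP's checking beyond Poisson noise;
- PCPs and clinics changing by different ratios between the two periods.

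The planned model has no term for either, so its standard error cannot reflect them. At stake is the interval and p-value for the outcome closest to what PMP integration is designed to change. An effect on checking could be reported with far more confidence than the data support.

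**Working it through.** The plan gives no mean, variance or power figure for PMP checks, so there is nothing to reproduce. The check compares the model's standard error with the true one when there is no intervention effect.

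**Inputs from the documents.** 48 clinics, equally allocated (section 17.2). Pooled groups of 24 v 24, as section 17.3 does for the primary models. 12 months before and 12 after (section 17.3). Two-sided 5% (section 17.2, stated for the power calculations only).

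**Assumed inputs.** 8 PCPs per clinic, 384 in all. Mean μ of 2, 5 or 10 checks per month. Log-scale SD of 0.3 for clinic and 0.8 for PCP intercepts. Month-level gamma noise with size k of 5 or 2, so that the variance-to-mean ratio at the mean, 1 + μ/k, runs from 1.4 to 6. SD s of a PCP's log change between periods of 0.2 or 0.3.

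**Step 1: model standard error.** With the intercepts cancelled, SE = √(sum of 1/total count over the four arm-by-period cells). Each cell expects 192 × 12 × μ = 2,304μ checks, so SE = √(4/(2,304μ)) = 0.0295, 0.0186 and 0.0132 at μ = 2, 5 and 10. Fitting the full nested Poisson mixed model to 12 simulated data sets at μ = 5 gave the same SE as the cell-count formula (0.01866 v 0.01866).

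**Step 2: month-level noise.** A cell total has variance Σλ + Σλ²/k. With the assumed intercepts, the average of λ² is μ² × exp(0.09 + 0.64) = 2.075μ². Hence (true SE/model SE)² = 1 + 2.075μ/k.

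**Step 3: unequal PCP change.** Each arm's log ratio gains variance 2.075s²/192. Hence (true SE/model SE)² = 1 + (2 × 2.075s²/192)/(4/(2,304μ)) = 1 + 12.45μs².

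**Step 4: type I error** = 2Φ(−1.96/ratio).

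| Setting | μ = 2 | μ = 5 | μ = 10 |
|---|---|---|---|
| Poisson given intercepts | 1.00, 5% | 1.00, 5% | 1.00, 5% |
| k = 5 | 1.35, 15% | 1.75, 26% | 2.27, 39% |
| k = 2 | 1.75, 26% | 2.49, 43% | 3.37, 56% |
| s = 0.2 | 1.41, 17% | 1.87, 29% | 2.45, 42% |
| s = 0.3 | 1.80, 28% | 2.57, 45% | 3.49, 57% |

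Simulation (1,500 null replicates per setting) agrees. The ratios were 1.37, 1.73 and 2.21 for k = 5; 1.80, 2.46 and 3.26 for k = 2; and 1.86, 2.56 and 3.57 for s = 0.3. With purely Poisson counts the ratio was 0.97 to 1.00 and coverage 95% to 96%. Across simulation runs that also cover s = 0.2, the range is about 1.3 to 3.6 for the ratio and about 13% to 58% for type I error.

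**Step 5: the remedies.** In the 1,500-replicate simulation, clinic-cluster-robust standard errors gave 93% to 95% coverage in every setting, including the purely Poisson one.

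A negative binomial model with only a PCP-by-period effect is not enough. Take a clinic-change SD of 0.1, a PCP-change SD of 0.3, a variance-to-mean ratio of 2 and μ = 10, with PCPs weighted equally. The noise variance per PCP is 2/120 + 2/120 = 0.033. The model's variance is 2 × (0.09 + 0.01 + 0.033)/192 = 0.00139. The true variance is 2 × (0.09 + 0.033)/192 + 2 × 0.01/24 = 0.00212. The ratio is √(0.00212/0.00139) = 1.23, and type I error is still about 11%.

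**The case against.** **The dispersion is unknown.** This stands. A reader might infer that the intervals are bound to be too narrow. The documents do not show that: they give no mean or dispersion for PMP checks and describe no pattern of monthly variation. If counts are Poisson given the intercepts, the planned analysis is valid. Unequal change is nevertheless contemplated, since section 17.3 plans to test whether clinician type and tenure moderate the effect. Section 5.5 also opens PMP integration to all clinics at month 6, within the 12-month post period.

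**The text does not say intercepts.** It says random effects for clinic and PCP. Intercepts are the ordinary reading, because no slope or period term is named.

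**The layout is assumed.** Section 11.1 says "We expect that 400-450 PCPs will be included in the final analytic samples for the analysis of EHR data and PDMP data", which is more than 384. The number of PCPs cancels from both ratio formulas, and the number of months cancels from the noise formula. With only 6 post months, the coefficient in step 3 falls from 12.45 to 2.075 × 1/(1/12 + 1/6) = 8.3. At s = 0.3 the ratio is then still √(1 + 8.3 × 2 × 0.09) = 1.6 at μ = 2 and √(1 + 8.3 × 10 × 0.09) = 2.9 at μ = 10.

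**The outcome is secondary.** This stands. A reader might infer that PMP checking is the decisive outcome for integration, or that a spuriously precise result led the DMC to open integration to all clinics. The documents support neither. Section 17.1 lists it as one of several key secondary outcomes to be presented, ties the formal boundary to the primary endpoint, and leaves substantial efficacy to be settled with the DMC. It gives no interim model for PMP checks. Section 5.5 does not say which outcomes the DMC saw.

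**Conclusion.** The point holds as a conditional one. The planned standard error for the arm-by-period effect on PMP checks is right only if monthly counts are Poisson given the intercepts and all PCPs and clinics change by a common ratio. The plan offers no protection if they do not. The size, about 1.3 to 3.6 times on the standard error and about 13% to 58% type I error, rests on assumed values: 2 to 10 checks per month, k of 2 to 5 or a PCP-change SD of 0.2 to 0.3, and the assumed intercept SDs. It is not an estimate for this trial. The primary prescribing and tapering analyses are untouched. The case for changing the plan is that the safer method performs properly whether or not the extra variation exists.

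**What to change.** In section 17.3, under the PDMP analysis, keep the Poisson mean model and state that inference for the interaction uses standard errors clustered by clinic, with a small-sample correction because there are about 48 clinics. The alternative is a negative binomial model, or a Poisson model with an observation-level random effect, with both PCP-by-period and clinic-by-period random effects. The clinic term is needed because clinics are the randomised units.

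The cost is a sentence or two of SAP wording, with no new data. Intervals will be wider if overdispersion or unequal change is present, and little is lost if neither is.
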